5 STUDY EVALUATIONS AND MEASUREMENTS

5.1 Screening and Monitoring Evaluations and Measurements

5.1.1 Medical or Research Record Review

For subjects who have participated in a study at the Center for Autism Research, their ASD diagnosis will be confirmed using previously collected information. The electronic medical records of subjects who receive care at CHOP may also be reviewed to confirm diagnosis. Finally, records supporting their ASD diagnosis will be requested from subjects who are not affiliated with CHOP. For subjects enrolled in Cycle B, research staff will review relevant records to confirm ASD status.

5.1.2 IQ testing

Cognitive function, including verbal and non-verbal intelligence, will be assessed using the Wechsler Abbreviated Scale of Intelligence, Second Edition (WASI-II; Wechsler & Hsiao-pin, 2011) or other equivalent IQ test. Subjects with a verbal and overall IQ greater than or equal to 75 (Cycle A), or 80 (Cycle B) will continue with the study.

5.1.3 Clinician Observed Autism Symptoms

Autism Diagnostic Observational Schedule - 2nd Edition (Lord, Rutter, DiLavore, Risi, Gotham, & Bishop, 2012). The ADOS-2 is a semi-structured standardized assessment using developmentally appropriate social interactions in a 30-45 minute evaluation session. The ADOS-2 consists of five different modules, each directed at a particular level of language ability. The ADOS-2 has been carefully psychometrically validated across a wide range of ages and severity levels in autism, and it is widely considered the single best gold standard diagnostic instrument. The ADOS will be administered onsite at CHOP during Cycle A. Feedback will be provided to participants in person or over the phone as needed, based on conversations between participating families and the study clinician. Participants who have completed an ADOS at the Center for Autism Research or a comparable organization within one year of participation in this study will not need to complete it again.

The ADOS will be audio and video recorded in accordance with CHOP Policy RI-2-03 (Recording or Filming of Patients). Audio and video recordings may be used for clinical supervision, training, educational, or research purposes.

5.1.4 Autism Screening

Social Communication Questionnaire (SCQ; Rutter, Bailey, & Lord, 2003). The SCQ is a parent report screening measure for ASD that has been validated for identifying children displaying autism symptoms. The SCQ will be completed by parents of participants.

Autism-Spectrum Quotient (AQ; (Ruzich et al., 2015)). The AQ is a widely used, 50-item self-report questionnaire designed to measure reciprocal behavior, social use of language, and other behaviors characteristic of ASD. Total AQ score and 5 subscales (communication, social skills, imagination, attention to detail, attention switching) are normally distributed, demonstrate good test-retest reliability, and have medium-to-high internal consistency (Baron-Cohen, Wheelwright, Skinner, Martin, & Clubley, 2001).

5.1.5 Other Measures and Questionnaires

Adult/Adolescent Sensory Profile (Brown, et al., 2001). The Adolescent/Adult Sensory Profile is designed as a trait measure of sensory processing patterns and effects on functional performance. An individual answers questions regarding how he or she generally responds to sensations, as opposed to how he or she responds at any given time. This enables the instrument to capture the more stable and enduring sensory processing preferences of an individual.

Child Behavior Checklist (CBCL) OR Adult Behavior Checklist, (T. Achenbach & Rescorla, 2001). The CBCL is a 118-item checklist completed by parents regarding a broad range of behavioral and emotional problems. Statements are rated from 0 to 2 based on how well the statement describes the youth: 0 (not true), 1 (somewhat or sometimes true) and 2 (very often true). Scores are reported for both internalizing and externalizing scales including the following subscales: Anxious/Depressed, Withdrawn/Depressed, Somatic Complaints, Social Problem, Thought Problems, Attention Problems, Rule-Breaking Behavior, and Aggressive Behavior. The Adult Behavior Checklist is a parent-report extension of the CBCL intended for adults aged 18-59. The Adult Self-Report is the self-report extension of the CBCL intended for adults aged 18-59.

Social Responsiveness Scale – Second Edition (SRS-2; Constantino, 2012). The SRS-2 distinguishes autism spectrum conditions from other psychiatric conditions by identifying presence and extent of autistic social impairment. The SRS-2 is a 65-item quantitative measure of autistic traits ranging continuously from significantly impaired to above average. Familial correlations of sub-clinical features of autism can be measured by the SRS-2, which is consistent with the potential for heritability of a broad autism phenotype in family members. Parents will complete the SRS-II or the SRS-ARV, as appropriate to the participant's age, as the measure of autistic traits in non-ASD and ASD participants. The SRS-2 will be completed by parents of subjects age 12-17.

Demographic and Medical History Form (all ages). Information about participant family, medical and diagnostic history, race/ethnicity, household income, and educational level will be collected from parents/adult participants. This information will be used to understand participant diagnostic history, control bias, and will be entered as covariates to statistical analyses when groups are not matched on critical features.

Police Knowledge Assessment. This measure has been created by study investigators to measure prior police interaction experience and feelings about interacting with police.

Police Interaction Behavior Checklist. This checklist has been created by study investigators as a learning tool to be given to all participants prior to beginning the first trial of the PSM. The Police Interaction Behavior Checklist describes how to appropriately behave while interacting with a police officer. The participant and the moderator can refer to this checklist as needed while progressing through the VR trials to aid in learning.

Floreo Feedback Questionnaire. This questionnaire has been created by study investigators to measure how the participants felt about the VR and to get feedback on how the VR can be modified to better suit people with different backgrounds.

5.2 Intervention: Virtual Reality Sessions

Each subject assigned to the PSM intervention will undergo three sessions over an approximately six week period (at least 24 hours between sessions). At the beginning of each session, research personnel will preview the VR session experience with the subject and a parent or caregiver as appropriate. The VR experience preparation will include screening of subject's health status and adjustment of the headset to fit the subject. The VR session will consist of multiple scenes in which the subject is approached and engaged by police officers in the virtual environment. Some police officer avatars in the virtual environment will be wearing facemasks to accurately reflect real-world masking behaviors in Cycle B. VR scenes will be presented via the Floreo application downloaded onto an iPhone worn by the participant in a lightweight, inexpensive VR headset. The VR interaction will be controlled and operated via linked iPad by a research staff member sitting with the subject at CAR in Cycle A, or via tele-administration in Cycle B. Subjects in the VR environment will receive live feedback from research staff members about police officer interaction expectations and safety in accordance with individual scene scripts and prompts. Each VR session should encompass four VR trials, each involving a non-identical police safety scene. The subject will take a break from the VR environment in between each trial.

5.3 Control Conditions

5.3.1 Cycle A: Video Modeling

Subjects assigned to the comparison video modeling interaction will undergo three sessions over a period of six weeks that will consist of BE SAFE The Movie Curriculum Lessons 1-4 (https://besafethemovie.com/curriculum/). The BE SAFE The Movie Curriculum consists of video-based instruction on police officer interaction expectations and safety. These include Lesson 1: Laws Help us BE SAFE; 2: Law Enforcement Officers Help Us BE SAFE; 3: Uniforms and Safety Tools; 4: Stay Calm When You Meet the Police; within each of these lessons, participants will be shown videos, and then complete additional engaging video-based activities and short movie scenarios to video model. The lessons will be presented by research staff member sitting with the subject at CAR. Video observation, activities, and modeling sessions will be structured to correspond with VR session duration and total number. Participants in the video modeling interaction arm will be screened for subject health status in preparation for their sessions.

5.3.2 Cycle B: Treatment-as-usual

Subjects assigned to the control condition will not receive any training with PSM, but will engage with the software for their assessments, and will continue their other treatments as usual. Participants in the treatment-as-usual arm will be screened for subject health status in preparation for their sessions.

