2.2 Secondary Objectives (or Aim)

The secondary objective is to demonstrate the efficacy of Floreo's PSM in adolescents and adults with ASD by assessing improvement in police interaction skills as compared to a treatment-as-usual condition under virtual implementation.

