5.4.1.2 Cycle B

Before beginning the first VR or video modeling intervention session, all participants will complete a baseline novel remote assessment of police interactions skills. These interactions are designed to measure each participant's ability to interact with a virtual police officer prior to completing either intervention. This assessment will include coded video recordings of participants wearing the VR headset while engaging in a standardized experience. The behaviors of the participant inside the virtual environment will also be coded. The interaction is designed with guidance from law enforcement officers with particular experience working with individuals with intellectual and developmental disabilities. The live interaction will be video-recorded via a CHOP-approved, HIPPA compliant videoconference platform. These recordings will be coded for a set of behaviors that would encourage successful police interactions (i.e.: making appropriate eye contact, etc.)

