5.4.2.2 Cycle B: Virtual Police Interaction Assessment

After the final VR intervention session, all participants will be assessed via a remote semi-structured interaction with a police or security officer avatar. Approximately 4weeks after the final VR intervention session, participants in Cycle B will be assessed once again via a remote interaction with a police or security officer. These interactions are specifically designed to serve as an index of behaviorally defined skills associated with effective interactions with a police officer. The police officer will be programmed with a semi-structured set of prompts to use when interacting with the participant, and will rate the participant's responses. The interaction is designed with guidance from law enforcement officers with particular experience working with individuals with intellectual and developmental disabilities. We will use video recordings of both the participant wearing the headset and behaviors while in the VR experience to code behaviors. These recordings will be coded for a set of both virtual and real-world behaviors that would

encourage successful police interactions (i.e. making appropriate eye contact, orienting to the virtual officer, etc.).

While it is important that our research participants are approached by simulated Police Officers, it is also critical that risks for stress/distress and other harms are minimized. To this end, the virtual reality Police Officer will take a casual, non-accusatory approach to questioning the participant, and will follow their standard procedures in the type of scenario where they need to inquire with an individual but where that individual is not a suspect.

Consistent with ethical standards in psychological research, all participants will be de-briefed immediately following the Remote Interaction Assessment. The research participant will be offered the opportunity to ask questions, and to provide their thoughts and feedback on the study procedures and practices. Research participants will also be asked to rate their experience with the remote Police Interaction, as well as the study process and procedures overall, in a formal questionnaire. Information gathered from both the interview and the questionnaire will be used to inform the researchers of how the practice is affecting research participants.

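### Cycle B takes its primary score inside the software that only the VR arm practises in, so that score cannot separate police interaction skill from platform familiarity

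*Combined protocol and SAP*

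**What the plan says.** **Exposure.** Under Section 5.2, VR subjects "will undergo three sessions over an approximately six week period". The same section adds: "Each VR session should encompass four VR trials, each involving a non-identical police safety scene". Training includes coaching: "Subjects in the VR environment will receive live feedback from research staff members about police officer interaction expectations and safety". Section 5.3.2 gives the TAU arm no such training: "Subjects assigned to the control condition will not receive any training with PSM, but will engage with the software for their assessments".

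**Outcome.** The Cycle B baseline (5.4.1.2) is done in the headset by both arms: "This assessment will include coded video recordings of participants wearing the VR headset while engaging in a standardized experience". After the intervention (5.4.2.2), "all participants will be assessed via a remote semi-structured interaction with a police or security officer avatar". Coding covers behaviours in the virtual scene and in the room. The examples given are "making appropriate eye contact, orienting to the virtual officer, etc". Sections 6.1 and 6.3.2 make this score, compared with baseline and between arms, the Cycle B primary endpoint.

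**Claim.** Section 2.2 states the aim as "assessing improvement in police interaction skills as compared to a treatment-as-usual condition under virtual implementation".

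**Safeguards.** Section 9.1.2 blinds the coders. Section 6.4 lists possible covariates, none of which concerns VR experience. No section says whether the assessment scenes may also appear in training.

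**The concern.** A randomised comparison attributes a difference to the assigned package as a whole. That is enough if the outcome measures the target skill equally well in both arms. Here the package includes repeated use of the measuring instrument. A VR subject reaches Visit 3 used to the headset, to looking around the scene and to being approached by an avatar. Some scored items, such as orienting to the virtual officer, could improve from that alone.

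At stake is the reading of Cycle B. The aim speaks of police interaction skills, and a reader will take that to mean encounters with officers. Section 5.4.2.1, written for Cycle A, itself argues that measurement needs real officers. Cycle B does not clearly plan such a measure: Section 6.2 names the virtual assessment at four weeks, while the hypothesis in 6.3.2 refers to live scores for that visit.

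**Working it through.** **1. Exposure before the Visit 3 assessment (Sections 5.2, 5.3.2, 5.4.1.2)**

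| | VR arm | TAU arm |
|---|---|---|
| Baseline assessment in headset | 1 | 1 |
| Training trials in headset | 3 sessions x 4 trials = 12 (planned) | 0 |
| Live coaching | yes | no |

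Section 9.4.2 puts VR time at about 20 minutes per session, so training adds about 3 x 20 = 60 minutes in the headset.

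**2. What the existing safeguards can do.** Baseline adjustment handles differences present before training; it cannot remove familiarity that one arm gains afterwards. Blinded coding prevents biased rating, but familiarity would change the performance itself.

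**3. The plan's own figure.** Section 6.4 gives a critical t of 1.99 and a detectable d of 0.74. A two-sample t-test with 48 per arm (df = 94) and two-sided alpha 0.05 has critical t = 1.9855 and, at 95% power, detectable d = 0.7435. So the figure reproduces with 48 per arm and 95% power; the power is not stated. The same section also gives 48 per study. With 1:1 allocation, which is not stated, that is 24 per arm, the value used below.

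**4. How far a pure familiarity shift could carry the test.** Let f be the shift in SDs of the analysed score, with a true skill effect of zero.

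- df = 2 x 24 - 2 = 46; critical t = 2.0129.
- Noncentrality = f x sqrt(24/2) = 3.464 f.
- P(significant, favouring VR) = P(T > 2.0129), where T is noncentral t with 46 df.

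| f (assumed) | Noncentrality | P(significant, favouring VR) |
|---|---|---|
| 0 | 0 | 0.025 |
| 0.1 | 0.346 | 0.053 |
| 0.2 | 0.693 | 0.100 |
| 0.3 | 1.039 | 0.173 |
| 0.4 | 1.386 | 0.273 |
| 0.5 | 1.732 | 0.396 |

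The smallest observed difference that reaches significance is 2.0129 x sqrt(2/24) = 0.58 SD.

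**5. Sensitivity to sample size.** With 48 per arm, the probability of significance in either direction is 0.077, 0.163, 0.307, 0.492 and 0.679 for the same five shifts. A larger trial does not cure the problem; it makes a given shift more likely to reach significance.

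**The case against.** The strongest reply is that the training is more than exposure. Staff coach VR subjects on what officers expect, and repeated experience of being approached is arguably the active ingredient. Behaviours in the room are coded as well as those in the scene. The knowledge questionnaire, which is not described as VR-based, is given before and after treatment. TAU subjects are not naive, since they wear the headset at baseline. The interface is also simple: Section 9.4.2 says the scene does not respond to walking, so much of the novelty may be spent at that first exposure. Finally, Section 2.2 limits the aim to virtual implementation, and Cycle A tests live-officer performance against an active comparator.

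Much of this stands. A reader might infer that skill and familiarity are wholly confounded, so that a positive Cycle B result would show nothing but comfort with the headset. The documents do not support that, because coaching could produce real skill gains and some of the evidence lies outside the virtual scene. A reader might also infer that assessment scenes are reused in training, or that TAU subjects get no help with the headset. The text is silent on both, and silence is not proof. It describes the Cycle B baseline assessment as new and standardised.

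The reply does not restore separability on the primary score. The questionnaire is secondary and measures knowledge. Virtual implementation can be read as the mode of delivery and need not limit the skill claimed. Cycle A has a different comparator, IQ threshold and set of subjects, so it cannot show that gains made in Cycle B carry over to live encounters.

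**Conclusion.** The point holds as a limit on interpretation. The primary Cycle B score cannot separate a gain in police interaction skill from a gain in platform familiarity, and a positive result does not by itself establish improvement outside VR. It would still be valid evidence that the VR package improves performance in a virtual police interaction relative to no PSM training.

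The size of any familiarity effect is unknown. The 5% to 40% range is illustrative and is not an estimate of bias in this trial. It rests on assumed shifts of 0.1 to 0.5 SD, zero skill effect, 24 per arm and a two-sided 5% t-test.

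The reading of the control arm relies on Section 5.3.2 as the governing text. Other places blur it: Section 3.1.3 gives three sessions to each condition, Table 1 marks VR sessions at every Cycle B visit without separating arms, and Sections 5.4.1.2 and 9.7 mention video sessions in Cycle B. These should be reconciled.

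**What to change.** - **Conclusion.** In Sections 2.2 and 6.3.2, word the Cycle B conclusion as performance in a virtual police interaction compared with no PSM training. Rest claims about real officers on Cycle A.
- **Supportive analysis.** Report the real-world coded behaviours separately from the in-headset ones, with the two lists fixed before coding. Section 5.4.2.2 already codes both. Label the analysis supportive so that it adds no confirmatory test. It helps only in part, because these behaviours are also recorded while the subject is in the headset.
- **Scenes.** State that scenes used at baseline, Visit 3 and follow-up are never used as training trials.
- **Optional.** Give both arms the same short headset orientation before baseline, with no police content. A few minutes cannot match about an hour of training, so this reduces the imbalance without removing it and does not replace the change to the conclusion.

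The cost is a narrower Cycle B claim, a little more analysis and, if the orientation is adopted, a few minutes at Visit 1. The comparator, sample size and primary endpoint stay as they are.

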5.4 Efficacy Evaluations

5.4.1 Baseline Assessment

5.4.1.1 Cycle A

Before beginning the first VR or video modeling intervention session, all participants will complete a baseline assessment of police interactions skills via a live role play of a police interaction with a study staff member. These interactions are designed to measure each participant's ability to interact with a police officer prior to completing either intervention. The study staff member will be provided with a semi-structured set of prompts to use when interacting with the participant. The interaction is designed with guidance from law enforcement officers with particular experience working with individuals with intellectual and developmental disabilities. The live interaction will be video-recorded via a videoconference platform. These recordings will be coded for a set of behaviors that would encourage successful police interactions (i.e.: making appropriate eye contact, etc.)

5.4.1.2 Cycle B

Before beginning the first VR or video modeling intervention session, all participants will complete a baseline novel remote assessment of police interactions skills. These interactions are designed to measure each participant's ability to interact with a virtual police officer prior to completing either intervention. This assessment will include coded video recordings of participants wearing the VR headset while engaging in a standardized experience. The behaviors of the participant inside the virtual environment will also be coded. The interaction is designed with guidance from law enforcement officers with particular experience working with individuals with intellectual and developmental disabilities. The live interaction will be video-recorded via a CHOP-approved, HIPPA compliant videoconference platform. These recordings will be coded for a set of behaviors that would encourage successful police interactions (i.e.: making appropriate eye contact, etc.)

5.4.2 Police Interaction Assessments

5.4.2.1 Cycle A: Live Police Interaction Assessment

After the final VR or video modeling intervention session, all participants will be assessed via a live semi-structured interaction with a police or security officer. These interactions are specifically designed to serve as an index of behaviorally defined skills associated with effective interactions with a police officer. The police officer will be provided with a semi-structured set of prompts to use when interacting with the participant, and will rate the participant's responses. The interaction is designed with guidance from law enforcement officers with particular experience working with individuals with intellectual and developmental disabilities. The live

interaction will be video-recorded. These recordings will be coded for a set of behaviors that would encourage successful police interactions (i.e. making appropriate eye contact, etc.).

Individuals with and without ASD both experience a degree of stress/anxiety when interacting with Police Officers. Police Officers also have particular characteristics, training, and expectations which make their approaches to members of the community unique. Furthermore, Police Officer approaches and interaction are very often unexpected. Yet, Police Officer approaches to civilians are common, every day occurrences, including for individuals with ASD. As a result of these factors, it is critical that experimental measurement of effective versus ineffective interaction with Police Officers in the current study are implemented using real Police or Security Officers.

While it is important that our research participants are approached by actual Police Officers, it is also critical that risks for stress/distress and other harms are minimized. To this end, the Police Officer will be instructed to take a casual, non-accusatory approach to questioning the participant, but to otherwise follow their standard procedures in the type of scenario where they need to inquire with an individual but where that individual is not a suspect. In addition, although the Police Officers will be blinded to the experimental treatment condition of the participant, all Police Officers will be made aware that the participants may have ASD, and will be given basic information and have opportunity to ask questions and learn about what it means for someone to have ASD.

Consistent with ethical standards in psychological research, all participants will be de-briefed immediately following the Live Interaction Assessment with the Police Officer. The researcher and the Police Officer will both remind the research participant that the Police Officer's approach to them was conducted as part of the study. The researcher and Police Officer will further explain to the research participant that they are not in trouble and that the Police Officer is not upset with them. The research participant will be offered the opportunity to ask questions, and to provide their thoughts and feedback on the study procedures and practices. Research participants will also be asked to rate their experience with the Live Police Interaction, as well as the study process and procedures overall, in a formal questionnaire. Information gathered from both the interview and the questionnaire will be used to inform the researchers of how the practice is affecting research participants.

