6.3.2 Efficacy Analysis

The primary analysis will be based on an intention to treat approach and will include all subjects randomized at Visit 1.

The primary efficacy endpoint will be the change in post-treatment Live Police Interaction Assessment Scores between the Virtual Reality Intervention and BE SAFE Video-Based intervention and the change in scores between the Baseline Assessment and Live Police Interaction Assessment. In the case of Cycle 2, the Baseline Assessment will be compared to the Virtual Police Interaction Assessment between the Virtual Reality Intervention and treatment-asusual groups. The study hypothesis is that participants randomly assigned to the Virtual Reality Intervention will perform better on the post-treatment Live or Virtual Police Interaction Assessment than will participants randomly assigned to the BE SAFE Video-Based intervention or treatment-as-usual condition.

The secondary endpoint will include changes in Police Interaction Knowledge Questionnaire Scores from Pre-Treatment to Post-Treatment for the Virtual Reality Intervention and BE SAFE Video-Based intervention or treatment-as-usual. The study hypothesis is that participants randomly assigned to the Virtual Reality Intervention will exhibit significantly greater improvement from Pre-Treatment to Post-Treatment on Police Interaction Knowledge Questionnaire than will participants randomly assigned to the BE SAFE Video-Based intervention condition or the treatment-as-usual condition. An additional Secondary endpoint is maintenance of learned skill improvements, indexed via the 4-week Follow-Up administration of the Virtual Police Interaction Assessment in Cycle B. The study hypothesis is that participants randomly assigned to the Virtual Reality Intervention will exhibit significantly greater Live Police Interaction Assessment Scores and skill improvement/maintenance 4-week follow-up than will participants randomly assigned to the treatment-as-usual condition.

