6.4 Sample Size and Power

This study will compare the PSM VR intervention to treatment-as-usual (TAU) in a total of 96 adolescents and adults with ASD, in two separate studies (i.e., n=48 per study). The most relevant study to date (Didehbani, Allen, Kandalaft, Krawczyk, & Chapman, 2016) included 30 7-16 year-olds with ASD in a pre/post virtual reality intervention to improve social cognitive skills. This study suggested a medium-to-large within-group effect of VR intervention on emotion recognition (Cohen's d = .63), but did not compare two interventions. Sensitivity analysis using G*Power indicated that intervention differences using our proposed sample size (N=48 per group) will be detected with a critical t of 1.99, and that we will be able to detect differences with effect sizes of Cohen's d = .74 or larger. Data will be behaviorally coded from video interactions and correct answers marked on knowledge tests. Scores will be summed, averaged, and examined for normality at the group level. Normally distributed data will be analyzed using parametric statistics (e.g., ANOVA, regression, Pearson correlation), and data that do not meet normality assumptions will either be transformed or will be analyzed using nonparametric statistical tests (e.g., Chi-square, Spearman correlation). Analyses will be corrected for comparisons. To compare PSM to BE SAFE, an Analysis of Variance (ANOVA) with Group (PSM VR Intervention, BE SAFE The Movie Video Modeling Intervention) as a Between-Subjects factor will be conducted for Live Interaction data. A separate ANOVA (or comparable statistical test) will be conducted for Questionnaire data. Relevant potential covariates include knowledge of police interactions at intake, sensory sensitivity scores, verbal abilities, and chronological age.

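### Cycle A's primary score depends on which officer runs the encounter, but officer is neither balanced over arms nor in the analysis; this mainly costs precision, and joint balancing and modelling would recover it cheaply

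*Combined protocol and SAP*

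**What the plan says.** Section 5.4.2.1 sets the Cycle A outcome measurement: "all participants will be assessed via a live semi-structured interaction with a police or security officer". The officer receives semi-structured prompts, is told to be casual and non-accusatory, and is told "to otherwise follow their standard procedures in the type of scenario where they need to inquire". The officer also rates the responses, and the encounter is video-recorded and coded. Officers are briefed on autism and blinded to condition. Section 9.1.2 repeats the blinding and extends it to the coders. Both sections speak of officers in the plural, but neither gives a number or a rule for assigning them.

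Section 6.3.2 makes this score the basis of the primary analysis: "The primary efficacy endpoint will be the change in post-treatment Live Police Interaction Assessment Scores". For the comparison with BE SAFE, section 6.4 says "an Analysis of Variance (ANOVA) with Group (PSM VR Intervention, BE SAFE The Movie Video Modeling Intervention) as a Between-Subjects factor will be conducted" on the Live Interaction data.

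Officer does not appear in any of the places where it could be handled:
- Section 9.1.1 names developmental age and sex as stratification variables (an open list).
- Section 6.4 lists four potential covariates, all participant characteristics.
- The rules for adjusting after an imbalance cover baseline characteristics (section 6.3.1) and participant variables (section 9.1.1).

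**The concern.** Each participant contributes one primary assessment, and the officer is part of the measuring instrument. An officer who is easier to talk to, or who rates more generously, shifts the scores of everyone that officer meets. The Cycle A baseline cannot remove this shift, because it is a role play with a study staff member (section 5.4.1.1).

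If the model ignores officer, that variation goes into the residual and widens the interval for the treatment difference. With 48 participants in the cycle there is little room for avoidable noise. A second possibility is that one arm systematically meets different officers from the other; officer style would then be mixed into the treatment contrast.

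**Working it through.** **1. The plan's own figure.** Section 6.4 plans 96 participants "in two separate studies (i.e., n=48 per study" but bases its sensitivity analysis on a different size: "using our proposed sample size (N=48 per group) will be detected with a critical t of 1.99". It states a detectable d of 0.74. For a two-sample t-test, power = P(|T| > t_crit), where T is noncentral t with 2n − 2 df and noncentrality d·√(n/2).
- n = 48 per group, two-sided 0.05: df = 94 and t_crit = 1.986. Detectable d is 0.578 at 80% power, 0.669 at 90% and 0.743 at 95%. The stated pair reproduces only at 48 per group with an unstated 95% power.
- n = 24 per arm (48 per study, 1:1 assumed): df = 46 and t_crit = 2.013. Detectable d is 0.826 at 80% power and 1.063 at 95%. Power at d = 0.74 is 0.709.

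The checks below therefore use 24 per arm, with d = 0.83 (about 80% power) and d = 0.74.

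**2. Assumptions not in the documents.** Officers: 2, 4 or 8. Officer share of outcome variance (ICC): 0.05 to 0.30. Effects are in within-officer SD units.

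**3. Size of the noise, by formula.** Ignoring officer shrinks the standardised effect by about √(1 − ICC), so the d detectable with 80% power becomes about 0.826/√(1 − ICC):
- ICC 0.05: 0.826/√0.95 = 0.848
- ICC 0.10: 0.826/√0.90 = 0.871
- ICC 0.20: 0.826/√0.80 = 0.924
- ICC 0.30: 0.826/√0.70 = 0.987

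**4. Power by simulation.** Here unbalanced means that officers are assigned at random, independently of arm. The d = 0.74 columns are for four officers; officer is a fixed factor where it is modelled.

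| ICC | d = 0.83, Group-only, unbalanced | d = 0.74, Group-only, unbalanced | d = 0.74, officer modelled, unbalanced | d = 0.74, officer balanced and modelled |
|---|---|---|---|---|
| 0.05 | 0.79 | 0.70 | 0.69 | 0.71 |
| 0.10 | 0.77 | 0.67 | 0.68 | 0.70 |
| 0.20 | 0.74 | 0.64 | 0.68 | 0.70 |
| 0.30 | 0.67-0.74 | 0.59 | 0.68 | 0.72 |

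The range in the last row of the d = 0.83 column reflects the number of officers. With officers balanced and modelled, power at d = 0.83 is about 0.79-0.81 at every ICC.

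**5. Type I error of the Group-only test at nominal 0.05** (ICC 0.05 to 0.30; 2, 4 or 8 officers).
- Officer independent of arm: 0.047-0.053.
- Officers exactly balanced over arms but not modelled: down to 0.026 (four officers) and 0.027 (eight officers) at ICC 0.30. Balancing takes officer variance out of the treatment difference but leaves it in the residual, so the test is conservative.
- Officer tied to arm, 70/30 split: 0.055-0.178.
- Officers wholly separate by arm: 0.086-0.550, highest with two officers and ICC 0.30.

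**6. Cost of fixed officer terms without balancing.** When officers hardly differ, the loss is about 2 points of power with four officers and 6-7 with eight.

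**The case against.** The strongest reply is that this is not a validity problem. Participants are randomised, officers and coders are blinded, both arms run at one centre, and video-modelling sessions are matched to VR sessions in length and number. If officer is independent of arm, chance imbalance is already in the standard error, and step 5 confirms a type I error near 5%. This stands.

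Three stronger readings are tempting, and the documents do not support them:
- **Officer differences would pass as a treatment effect.** This needs a systematic link between officer and arm. No section describes one. None excludes one either, so it remains a condition and not a finding.
- **Officers are booked once the arm is known.** The documents do not say when Visit 3 or its officer is scheduled.
- **The protocol concedes that its officers differ from one another.** The sentence in section 5.4.2.1 about officers' characteristics and training contrasts police with other people, not one officer with another.

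It is also fair that officers do not simply do as they please: prompts, an instructed approach, a common briefing and blinded coding all standardise the measurement. These limit variation, but an officer's manner can still change the behaviour that is later coded, and the officer's own rating is also collected. Nor is the model closed to adjustment, since sections 6.3.1, 6.4 and 9.1.1 allow covariates. Those provisions concern participants, so they would not bring officer in.

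Finally, the ICC and the number of officers are assumed. At an ICC of 0.05 the loss is only about a point.

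**Conclusion.** The gap is real and of modest size. A source of variation built into Cycle A's primary measurement is left out of both design and analysis. At 24 per arm and d = 0.83 the cost is about 1 to 6 points of power for ICC 0.05 to 0.20, and about 6 to 13 points at ICC 0.30. The Group-only test remains valid if officers are assigned independently of arm. Inflated false positives are a contingent risk that a rostering rule would remove.

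The conclusion rests on 1:1 allocation, more than one officer (implied by the plural, not stated), and assumed ICCs. With a single officer the point falls away.

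**What to change.** For Cycle A:
1. State the number of officers. If there is one, say so and stop there.
2. Otherwise roster officers without reference to arm and balanced across the two arms. Whoever holds the allocation list should do the balancing, so that officers stay blinded.
3. Record officer ID for every Live Police Interaction Assessment.
4. Add officer to the primary model: a fixed factor if officers are few, otherwise a random intercept with a small-sample degrees-of-freedom correction such as Kenward-Roger. The correction matters because an uncorrected random intercept gave 5-8% false positives in a simulation with four officers and a 75/25 imbalance over arms.

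Steps 2 and 4 belong together. Balancing without the model term makes the test conservative (step 5 of the working), and fixed terms without balancing can cost power (step 6).

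The cost is one data column, one rostering rule and one model term. With four officers as a fixed factor, residual df go from 46 to 46 − 3 = 43. If assessments are already complete, officer ID may be recoverable from the video recordings; balance could then only be described, and officer should be modelled with the cost in step 6 in mind.
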